## 1 DOCUMENT CHANGE HISTORY

Version number	Version date	Author	Description of change(s)
[REDACTED]	[REDACTED]	[REDACTED] [REDACTED]	[REDACTED]
[REDACTED]	[REDACTED]	[REDACTED]	[REDACTED] [REDACTED]
[REDACTED]	[REDACTED]	[REDACTED]	[REDACTED] [REDACTED]
1.3	05june2020	[name]	[REDACTED] [REDACTED] [REDACTED]

### **Disclaimer**

This study will be conducted for research purposes only.

## 2 INTRODUCTION

Multifocal contact lenses provide correction for vision at near as well as in the distance. This segment of the contact lens market has been slowly growing as more products become available.

CooperVision is interested in comparing the performance of their newly developed daily disposable (DD) MyDay® Multifocal (Lens A) contact lens to patients' habitual multifocal lenses and to the competitor product DAILIES TOTAL1® Multifocal (Lens B). Of particular interest is the comparison of handling the lenses, which includes insertion and removal to and from the eye. Ease of lens handling is critical in a presbyopic population who require specific prescription for seeing well up close.

## 3 OBJECTIVES

The objective of the study is to compare the lens handling and performance of Lens A to habitually worn multifocal contact lenses and to the competitor Lens B.

The primary outcome variable for this study is:

- Subjective at-home ratings of 'Lens handling for insertion', using a 0-10 scale, collected on Day 13.

## 4 HYPOTHESIS

The null hypothesis is that there will be no difference between the at-home subjective ratings of 'Lens handling for insertion', collected on Day 13 for Lens A compared to Lens B.

## 5 MATERIALS AND METHODS

### 5.1 STUDY DESIGN

#### 5.1.1 OVERALL DESIGN

This is a prospective, randomized, participant-masked, crossover, bilateral dispensing study conducted at up to 5 clinical practice sites in the United States, listed on page 3. Each lens type will be worn for up to 3 weeks. The lens prescription of each lens type will be optimized after 3-7 days wearing experience, prior to starting a 2-week wear period.

#### 5.1.2 RANDOMIZATION

Participants will be wearing their habitual lenses during the first 2-week phase, followed by a randomized order of Lens A and Lens B lens wear.

A randomization schedule will be generated for each site using a web-based program to determine the order of Lens A and Lens B lens wear: ([www.randomization.com](http://www.randomization.com)). The final study randomization schedule will be generated by CORE's Database Administrator and provided to the research assistants at each site.

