## 5.2 INVESTIGATIONAL SITES

### 5.2.1 NUMBER OF SITES

---

This study will be conducted at 5 optometry practice sites, listed on page 3 of this document.

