## 5.3 STUDY POPULATION

### 5.3.1 SAMPLE SIZE CALCULATION

The sample size was calculated using lens handling data from a previous study comparing Lens A against lens B (CooperVision, data on file). In that study a 0-100 scale was used, not the 0-10 used in this study. As a way of compensating for fewer step sizes in the 0-10 scale, a target difference of 5 units on the 0-100 scale was chosen as a meaningful clinical difference in 0-100 subjective responses.

Using the 0-100 scale data described above for 'lens handling for insertion', where the data showed a standard deviation of 12.7 and when applying requirements of 80% power and alpha 0.05 in a two-tailed t-test, a minimum sample size of 53 participants is recommended in order to detect a mean difference of 5 units.

To account for dropout, up to 60 participants may be randomized and dispensed with study product in total, with the target of at least 53 completing the study.

Note: this study will use a subjective rating scale of 0-10, integer steps.

[figure not shown]

Figure 1: Sample size calculation graph

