## 12 STATISTICAL ANALYSIS AND DATA MANAGEMENT

### 12.1 STATISTICAL ANALYSIS

All data will be analyzed by CORE at the University of Waterloo. Unmasked data analysis will be conducted using Statistica 10, Statsoft or other suitable software. Descriptive statistics will be provided on demographic data (age, gender, refractive error distribution, etc.). Table 7 lists the primary and other outcome variables and anticipated statistical procedures.

Comparisons will be made between the study lenses for the variables measured at the 2-week visits. Additionally the subjective ratings completed on day [REDACTED] 13 of each phase will be compared. A binomial test will be used to analyze the results for the count data [REDACTED]  
[REDACTED] Where relevant, the number of “neither agree or disagree” responses will be evenly distributed to the two options on the basis they would be equally likely to choose either.

Where appropriate, data may be presented as both mean and as counts by ‘bucket’ groups.

Table 6: Statistical procedures

Variable	Analysis	Statistical test
Ratings: Likert & Preference	Comparison between study days and/or between contact lenses per time point.	Freidman ANOVA Wilcoxon matched pairs test
Ratings: numerical ratings Biomicroscopy	Comparison between study days and/or between contact lenses per time point.	Freidman ANOVA Wilcoxon matched pairs test RMANOVA
Demographics Lens fit variables	Descriptive stats	One or more: mean, median*, mode, standard deviation, minimum, maximum, frequency count

\* For non-parametric data only

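### Lens order is randomised separately at each site, but no readable planned test accounts for sequence (period) or site

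*Combined protocol and SAP*

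**What the plan says.** Section 5.1.1 describes the design: "This is a prospective, randomized, participant-masked, crossover, bilateral dispensing study conducted at up to 5 clinical practice sites". Section 5.2.1 gives the number of sites as five. After a habitual-lens phase, participants wear the two study lenses in randomised order, and section 5.1.2 states that "A randomization schedule will be generated for each site using a web-based program", which sets that order. The word stratified is not used, but a separate schedule per site amounts to stratification by site.

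The null hypothesis in section 4 is "no difference between the at-home subjective ratings of 'Lens handling for insertion', collected on Day 13 for Lens A compared to Lens B".

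For numerical ratings, Table 6 in section 12.1 describes the analysis as "Comparison between study days and/or between contact lenses per time point" and lists Friedman ANOVA, Wilcoxon matched pairs and repeated-measures ANOVA. The terms of the repeated-measures model are not given. No readable text names sequence, period or site as a factor, block or stratum. Section 12.1 presents the table as anticipated procedures and is partly redacted, so this point rests on what can be read.

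**The concern.** An analysis would normally reflect the factors built into the randomisation. Here these are lens order and, through the separate schedules, site.

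The within-person comparison removes some of the problem. If one practice's participants rate everything higher, that cancels in each person's A-B difference. Two things do not cancel:

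- **A common period effect.** If ratings drift between the first and second study-lens phases, for example through practice at handling, the drift adds to the difference in one order and subtracts from it in the other. Unmodelled, it widens the error term, and it shifts the estimate if the two orders have unequal numbers.
- **Site differences in the A-B contrast.** These are possible because section 5.1.3 says investigators cannot be masked, and they fit and optimise both lenses. Unmodelled, this variation is pooled into the SD of the difference.

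At stake are some precision and, under uneven orders, a small shift in the estimate.

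**Working it through.** **Inputs.** From section 5.3.1: difference 5 and SD 12.7 on the 0-100 scale, two-sided alpha 0.05, power 80%, n = 53. From section 5.2.1: five sites. The documents give no between-site share of variance, site sizes, period effect or AB/BA split, so those below are assumptions.

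**1. The plan's own figure.** The plan states that "a minimum sample size of 53 participants is recommended in order to detect a mean difference of 5 units". Take 12.7 as the SD of the paired difference. Then SE = 12.7/√53 = 1.744 and the noncentrality is 5/1.744 = 2.866. With 52 degrees of freedom the noncentral t power is 80.3%, and 53 is the smallest n that reaches 80%. The stated size is reproduced with no period or site term.

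**2. Cost of the extra terms if they explain nothing.** Site uses 4 degrees of freedom and sequence 1. With the SE held at 1.744:

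- 52 df (neither term): 80.3%
- 48 df (site): 80.2%
- 47 df (site and sequence): 80.2%

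The unrounded loss for both terms is 80.31 − 80.16 = 0.15 point. This holds for near-equal orders. With an assumed 30/23 split, SE = 12.7 × √[(1/30 + 1/23)/4] = 1.760 and power at 47 df is 79.5%.

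**3. Period effect.** Let δ be the mean rating in the first study-lens phase minus that in the second. The expected A-B difference is τ + δ in order AB and τ − δ in order BA. Without a sequence term:

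- The estimate is shifted by δ(n_AB − n_BA)/N. With 30/23 this is 7δ/53 = 0.13δ, or 0.26 units for an assumed δ of 2.
- With near-equal orders the variance of the differences rises by about δ². For δ = 2 the SD goes from 12.7 to √(161.29 + 4) = 12.86, and power is about 79.4%. This treats 12.7 as free of period variation, which the documents do not say.

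**4. Gain from fitting site.** Let ρ be the share of A-B variance lying between sites. The simple formula uses SD 12.7√(1 − ρ) and 48 df, giving 82.2% at ρ = 0.05 and 84.1% at ρ = 0.10. Setting these against 80.3% overstates the gain. With five fixed sites the mean difference varies only through within-site error, so the test without site already does better than 80.3%. A simulation of 20,000 runs, with assumed site sizes 11/11/11/10/10, gave:

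| ρ (assumed) | Power without site | Power with site | Gain (points) | Type I error without site |
|---|---|---|---|---|
| 0.05 | 81.3% | 82.3% | 1.0 | 0.046 |
| 0.10 | 82.0% | 84.2% | 2.2 | 0.045 |
| 0.20 | 84.3% | 88.4% | 4.1 | 0.033 |

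**5. Weighting of sites.** If the lens effect is averaged equally over sites, SE = (12.7/5) × √Σ(1/n_i). With no site variance and 48 df:

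- Sizes 14/12/11/9/7: Σ(1/n_i) = 0.4996, SE = 1.795, power 77.9%.
- Sizes 18/13/10/7/5: Σ(1/n_i) = 0.5753, SE = 1.927, power 72.0%.

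Weighting by site size keeps SE at 12.7/√53 = 1.744 and power at 80.2%.

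**The case against.** The strongest reply is that a within-person crossover with five small sites hardly needs site in the model. The true between-site share may be zero. If the earlier study's SD of 12.7 already pooled several sites, the 53 already budgets for this variation. Table 6 is only anticipated, and a repeated-measures ANOVA could carry a site factor. A site term that averages sites equally can also lose more power than it gains when recruitment is uneven.

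Much of this stands. The between-site share is unknown, so the gain is conditional. The warning about equal weights is right and governs the form of the fix. The SD question cannot be settled from the documents. If 12.7 were a within-site SD, the simple formula would put power without site at 78.3% (ρ = 0.05) or 76.1% (ρ = 0.10), against 80.2% with site, though it overstates that loss for the reason given in step 4. The reply does not remove the gap: sequence, period and site appear in no readable analysis text, and the Wilcoxon and Friedman tests as listed carry none of them.

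A reader might also infer three stronger points that are not supported:

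- **That omitting site makes the test anti-conservative.** For these five sites it is slightly conservative (0.033 to 0.046 in the simulation).
- **That adding site removes a site-by-period shift.** It does not. Sequence and site main effects fit one common period effect, and a shift confined to one site would need a site-by-sequence term. The documents also do not show uneven orders within sites; they are silent on blocking.
- **That a fixed site term supports inference to other practices.** With random site-by-lens effects at ρ = 0.05, simulated type I error was 0.105 without site and 0.112 with it.

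**Conclusion.** The point holds as a minor improvement. Lens order is randomised within site, and no readable planned test uses sequence, period or site. A common period effect and site differences in the A-B contrast would therefore stay in the error term, and a period effect would move the estimate in proportion to any AB/BA imbalance.

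Fitting both factors costs about 0.1 to 0.2 power point at 53 completers with near-equal orders and no site or period variation. Fitting site gains about 1 to 2 points if 5% to 10% of the A-B variance lies between sites, a share that is assumed. The conclusion also assumes that 12.7 is the SD of the paired difference, which reproduces the stated 53, and that nothing in the redacted part of section 12.1 supplies the missing terms. It does not show that the trial is underpowered or that its type I error is wrong.

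**What to change.** In section 12.1, name one primary analysis: a linear model of each participant's Day 13 A-B difference in insertion handling, with sequence (which carries the period effect) and site as fixed factors. Average the lens effect equally over the two orders, so that period drops out, and weight it over sites by site size, not equally. Report the A-B difference by site descriptively.

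If a rank test is kept as primary, stratify it by site and sequence. One way is to compare the phase differences (first study-lens phase minus second) between the two orders with a rank-sum test stratified by site. If the sponsor prefers to leave site out, a sentence giving the reason should be added, and sequence should still be fitted.

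The change costs 5 degrees of freedom and a few lines of text. It needs no new data, visits or participants.

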### 5.1.3 MASKING

---

Participants will wear their habitual lens with an optimized prescription during the first Phase, followed by a masked lens wear using Lens A and Lens B. Lens packages/foils will be over-labeled with strongly adhesive stickers to mask the participant to the lens brand.

It is not possible for the study investigators to be masked because of the need to follow the specific lens fitting guide during the lens prescription optimization visit (Visits 0, 2-1, 3-1).

## 5.2 INVESTIGATIONAL SITES

### 5.2.1 NUMBER OF SITES

---

This study will be conducted at 5 optometry practice sites, listed on page 3 of this document.

### 5.2.2 INVESTIGATOR RECRUITMENT

---

The principal investigator at each site will be required to fulfil the following criteria:

- Is a licensed Optometrist with at least two years of contact lens fitting experience.
- Can demonstrate training in Good Clinical Practice (GCP) by the already trained principal investigator.
- Accepts responsibility for the conduct of the study at their site.
- Has in-office email and either document scanning capabilities or fax.
- Will scan and send all study visit documents to CORE, ideally the same day\* as the visit or at most within 2 days of the study visit.
- Is willing to follow the study protocol and to co-operate with the study monitors at CORE.

\* Study documents are required as soon as possible because this allows for prompt lens ordering and timely data review, query and entry.

## 5.3 STUDY POPULATION

### 5.3.1 SAMPLE SIZE CALCULATION

The sample size was calculated using lens handling data from a previous study comparing Lens A against lens B (CooperVision, data on file). In that study a 0-100 scale was used, not the 0-10 used in this study. As a way of compensating for fewer step sizes in the 0-10 scale, a target difference of 5 units on the 0-100 scale was chosen as a meaningful clinical difference in 0-100 subjective responses.

Using the 0-100 scale data described above for 'lens handling for insertion', where the data showed a standard deviation of 12.7 and when applying requirements of 80% power and alpha 0.05 in a two-tailed t-test, a minimum sample size of 53 participants is recommended in order to detect a mean difference of 5 units.

To account for dropout, up to 60 participants may be randomized and dispensed with study product in total, with the target of at least 53 completing the study.

Note: this study will use a subjective rating scale of 0-10, integer steps.

[figure not shown]

Figure 1: Sample size calculation graph

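### Do the move from 0-100 planning data to 0-10 integer ratings, and the lack of one named Lens A versus Lens B test, undermine the sample size of 53?

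*Combined protocol and SAP*

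**What the plan says.** Section 5.3.1 sizes the trial from an earlier Lens A versus Lens B study that used a 0-100 handling scale, "where the data showed a standard deviation of 12.7". With 80% power, two-sided alpha of 0.05 and a t-test, it concludes that "a minimum sample size of 53 participants is recommended in order to detect a mean difference of 5 units". Up to 60 participants may be randomized, with at least 53 expected to complete.

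The change of scale is disclosed. The section explains its target this way: "As a way of compensating for fewer step sizes in the 0-10 scale, a target difference of 5 units" on the 0-100 scale. It closes with "Note: this study will use a subjective rating scale of 0-10, integer steps".

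The hypothesis in Section 4 concerns the at-home insertion-handling rating "collected on Day 13 for Lens A compared to Lens B". Section 5.1.2 sets out three wear phases: "Participants will be wearing their habitual lenses during the first 2-week phase, followed by a randomized order of Lens A and Lens B lens wear".

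Section 12.1 says its table "lists the primary and other outcome variables and anticipated statistical procedures". The table is captioned Table 6, although the text calls it Table 7. Its row for numerical ratings reads "Freidman ANOVA Wilcoxon matched pairs test RMANOVA". Parts of Section 12.1 are redacted, but this row is legible.

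**The concern.** There are two worries.

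The first is power. The calculation belongs to one measurement scale and the trial uses another. Rounding answers to whole numbers adds noise, which raises the SD of within-person differences and lowers power. The text says the 5-unit target compensates for the coarser scale, but 53 was computed for those same 5 units (0.5 points on the new scale), so the target leaves nothing in reserve. As 53 is the smallest number that reaches 80%, any extra noise takes power at exactly 53 below the stated level.

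The second is the test. Three procedures are listed as anticipated, with no rule for choosing and no row for the primary outcome, and the analysis is unmasked. With three lens conditions, Friedman or a three-lens RMANOVA is an overall test and does not by itself answer the Lens A versus Lens B question. The t-test used for sizing is not listed by name. An analyst could in principle pick the test after seeing the results, on the trial's only stated hypothesis.

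**Working it through.** **Inputs from Section 5.3.1.** Difference 5 and SD 12.7 on the 0-100 scale; two-sided alpha 0.05; power 80%; 53 completers; at most 60 randomized. The words paired and SD of differences do not appear. They are inferred from the crossover design and from the fact that they reproduce the figure.

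**1. Reproduce 53.** For a paired t-test the noncentrality is (difference / SD) × √n.

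- n = 53: (5 / 12.7) × √53 = 2.866, power 80.3%.
- n = 52: (5 / 12.7) × √52 = 2.839, power 79.5%.

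So 53 is the minimum. Two independent groups would need about 103 per group, which rules that reading out.

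**2. Effect of rounding, under stated assumptions.** On the 0-10 scale the target is 0.5 and the SD is 1.27. Rounding to the nearest integer adds a variance of about 1/12 per rating, so 2/12 per difference. Answers already given in fives carry part of that noise (0.25/12 per rating), and answers given in tens carry all of it. How finely the earlier answers were graded is not stated, so each case is an assumption.

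| Earlier answers | SD of differences | Power at 53 (paired t) | Difference detectable at 53 with 80% power |
|---|---|---|---|
| Finely graded | √(1.27² + 2/12) = 1.334 | 76.4% | 0.52 |
| In fives | √(1.27² + 2/12 − 2 × 0.25/12) = 1.318 | 77.3% | 0.52 |
| In tens | 1.27 | 80.3% | 0.50 |

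Simulations with a ceiling at the top score, calibrated so that the observed 0-100 differences have mean 5 and SD 12.7, agree to within about two points of these figures. For roughly normal ratings, Wilcoxon is about one point lower. With heavier-tailed, finely graded differences it reaches 79-80%, while the paired t-test stays at about 76%.

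**3. The model builds in a loss.** The table assumes that each participant forms a 0-100 answer and then rounds it. Someone asked a 0-10 question directly need not do that, and the SD may be smaller or larger than 1.27. At n = 53 and a difference of 0.5, SD 1.20 gives 84.5% and SD 1.35 gives 75.4%. The rounding shift is 1.334 − 1.27 = 0.064, about the same size as these changes of 0.07 to 0.08 in the planning SD.

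**4. Room within the plan.** The 53 is a floor, and 60 − 53 = 7 further participants may be randomized. In the finely graded case, paired t power is 80.1% at 58 completers and 81.5% at 60. For a full scale step (1 point), power at 53 exceeds 99%.

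**5. The unnamed test.** RMANOVA restricted to Lens A and Lens B is the paired t-test (F = t²), which matches the sizing. Wilcoxon matched pairs compares the same two ratings and is also valid. As a worst case, suppose the analyst always reports the smaller p-value of the two. Simulating no difference between lenses, with n = 53, integer ratings capped at 10, mean ratings of 7 to 9, within-person correlations of 0.3 and 0.6, and 20,000 runs per setting, gives a type I error of about 5.1% to 5.6%. The tests are so highly correlated that choosing between them gains little.

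**The case for a change.** The strongest case for a change is that the edits cost almost nothing and would replace assumptions with facts. The sponsor holds the earlier data, so rounding them to 0-10 and restating power would settle the range. Naming one primary test would remove any later choice. Read as a power adjustment, the compensating sentence is wrong whatever grading is assumed.

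Some less favourable scenarios also exist. By a large-sample efficiency argument, Wilcoxon with full rounding noise has about 74% power at 53 and needs about 61 completers for 80%, just above the maximum of 60. If the 5 and 12.7 described an unbounded underlying scale, a ceiling with mean ratings near 9 would bring power down to about 65-74%.

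What stands: the plan shows no power on its own scale, the compensating sentence is loosely worded, and the readable text names no single primary test. What does not stand is that these alter the trial. Section 5.3.1 presents 12.7 as what the data showed, so the bounded, observed-data calibration is the apt one, and the lower ceiling figures rest on a different premise. The Wilcoxon shortfall assumes near-normal differences and full rounding noise together. The compensating sentence can also be read as explaining why a target of half a scale step was chosen, which is a reasonable way to be cautious.

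**Conclusion.** The concern does not call for a change. The 53 is correct for the calculation described, and the change of scale is stated openly. A shortfall on the 0-10 scale is possible but not shown: power at exactly 53 completers is about 76% if finely graded answers are rounded and 80% if the SD of 1.27 carries over, and could be higher if the SD is smaller on a directly answered scale. The rounding loss is 0 to about 4 points for the paired t-test, or 0.02 points in detectable difference, and is gone at 58 to 60 completers. That is no larger than ordinary uncertainty in a planning SD.

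The missing test name is a gap that an analyst can fill sensibly from the plan's own table, with Wilcoxon or a two-lens RMANOVA. The choice between them is a fair trade-off that depends on the shape of the ratings, and exploiting it would add only about half a point to the type I error. A tidier Section 5.3.1 and a named test would read better, but neither enrolment nor the completer target would change, nor would what the trial can conclude.

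This rests on the inferred paired reading of the SD, on rounding to the nearest integer, and on 5 and 12.7 describing ratings as observed.
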